Appendix 2 SAS code for Efficacy Analyses

A. CR/CRh Rate

The SAS® code (SAS Version 9.3 or more current) of the following form will be used for the CR/CRh rate estimate along with confidence interval.

proc freq data=DATA_NAME ;
 by COHORT;
 tables OUTCOME / exact binomial (p=0.15);
 weight count;
 exact binomial;

run;

Where DATA_NAME is the name of the dataset, COHORT is a vector containing treatment group assignment; OUTCOME is a vector containing the investigator response for each patient.

B. EFS, DOR and OS

The following SAS® code (SAS Version 9.3 or more current) will be used: proc lifetest data=DATA_NAME; time OSTIME*CENSOR(1); id COHORT;

run;

Where DATA_NAME is the name of the dataset, OSTIME is a vector containing the OS measurement for each patient, CENSOR is its respective censoring vector (1=censored, 0=non-censored event), COHORT is a vector containing cohort assignment.

```
The following SAS® code (SAS Version 9.3 or more current) will be used for OS:
proc lifetest data=DATA_NAME plots=(s, ls, lls) intervals=3, 6, 12, 24;
time OSTIME*CENSOR(1);
id COHORT;
```

run;

		Single Agent			Combination						
			Total FT-		Phase 1						
	FT-2102		2102	FT-2102 150 mg	FT-2102 +	Total FT-2102 +					
	150 mg	Phase 1 FT-2012	Single	BID+ Azacitidine	Azacitidine	Azacitidine 75					
Parameter	BID	Single Agent	Agent	75 mg/m2	75 mg/m^2	mg/m ²	Overall				

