Cohort 1 (patients with R/R AML harboring IDH1-R132 mutations): A group sequential design is planned for this cohort with two interim analyses and a final test. One hundred

seventy-three (173) patients provide 90% power to test the null hypothesis that the true complete response rate (CR + CRh) is 15% or less versus the one-sided alternative hypothesis that the true complete response rate is greater than 15%, assuming a true response rate of 25%, with a 2.5% significance level using a one-sided exact test for a binomial proportion.

Two interim analyses are planned, at approximately 33% and 67% of the information, respectively. O'Brien-Fleming stopping boundaries will be used for both alpha and beta adjustments. At the first interim, if $\leq 6/58$ responses are observed (or crude p-value ≥ 0.88), the trial may be stopped early for futility. Interim analysis 1 spends 0 alpha and 0.004 beta. The first interim analysis will be conducted on the full analysis set (FAS) within Phase 2 Cohort 1. At the first interim analysis the study is not intended to stop for efficacy. At the second interim analysis, if $\geq 28/115$ responses are observed (or crude p-value is ≤ 0.0057), the trial may stop enrollment for efficacy and if there are 20 or fewer responses (or crude p-value is ≥ 0.2718) the trial will be stopped for futility. Interim analysis 2 spends 0.006 alpha and 0.044 beta. The second interim analysis will be conducted in the efficacy evaluable (EE) analysis set within Phase 2 Cohort 1.

In the event of an early stop for efficacy, all enrolled patients would remain on treatment and their long-term efficacy data, such as, EFS and OS, will continue to be observed.

If the study is not stopped early for efficacy or futility, at least 173 evaluable patients are planned to be enrolled. A one-sided exact test will be performed. If the one-sided p-value is \leq 0.0245, the null hypothesis (the response rate is \leq 15%) will be rejected, and the alternative hypothesis that the response rate is > 15% will be accepted. If exactly 173 patients are evaluable, this is equivalent to 36 or more responses observed.

To account for discordance between central and local testing of the IDH1-132 mutation, approximately 190 patients are planned to be enrolled into this cohort.

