Cohort 7 (treatment naïve AML patients for whom standard treatments are contraindicated): A Simon's optimal two-stage design will be used. The null hypothesis that the true complete response rate is 25% will be tested against a one-sided alternative. In the first stage, 17 patients will be evaluated. If there are 5 or fewer complete responses in the first 17 patients, the study will be stopped. Otherwise, 37 additional patients will be accrued for a total of 54 patients. The null hypothesis will be rejected if 20 or more complete responses are observed in these 54 patients. This design yields a 1-sided type I error rate of 0.025 and power of 80% when the true complete response rate is 45%.

Cohort 8 (treatment naïve AML patients who are candidates for azacitidine first line treatment): A Simon's optimal two-stage design will be used. The null hypothesis that the true complete response rate is 25% will be tested against a one-sided alternative. In the first stage, 7 patients will be evaluated. If there are 2 or fewer complete responses in the first 7 patients, the study will be stopped. Otherwise, 21 additional patients will be accrued for a total of 28 patients. The null hypothesis will be rejected if 12 or more complete responses are observed in these 28 patients. This design yields a 1-sided type I error rate of 0.025 and power of 80% when the true complete response rate is 55%.

D. Treatment Randomization

No randomization is planned.

E. Assessment Schedule

See Appendix 1 for a detailed study Schedule of Events, including measurements and evaluations for the entire study period. All planned assessments will be performed predose with the exception of postdose PK/PD sample collection and ECG.

V. Interventions

A. Clinical Trial Material

FT-2102

FT-2102 Capsules are initially presented as two unit strengths, 50 or 150 mg, for oral administration. FT-2102 will be administered as a fixed dose. In case of BID dosing, FT-

2102 should be taken every 12 hours with a minimum of 8 hours between doses. When administered in combination with azacitidine, with the exception of C1D1 and C2D1 (when PK sampling is performed), it is recommended that FT-2102 should be administered first on the days when both FT-2102 and azacitidine are given. The protocol provides additional product details in Section 5.

Following provide dose-escalation schema.

- Single-Agent Dose-Escalation Schema
 - 1. 150 mg QD
 - 2. 300 mg QD
 - 3. 150 mg BID

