RFS, EFS, OS, TTCR/CRh, TTCR, TTR, DCR/CRh, DCR, DOR: Time to event endpoints listed here will be expressed as the number of months from first dose to the event and will be analyzed using Kaplan-Meier (KM) methods for each cohort, with the exception of TTCR/CRh, TTCR, and TTR, since these analyses are performed only on the subset of responders and censoring is unnecessary. The analysis will include median, 1st and 3rd quartiles for time calculated using Kaplan-Meier methods, and the 95% confidence interval for the median

calculated using the Brookmeyer-Crowley method. The estimated probability of survival over time for RFS, EFS, OS, DCR/CRh, DCR, and DOR will be plotted as KM curves for Phase 2 Cohort 1, with the exception of RFS, which will be performed for Phase 2 Cohort 2 only. Appendix 2 provides the SAS code.

The survival probability and 95% confidence interval will be estimated at selected landmark timepoints of: 3 months, 6 months, 12 months, and 24 months based on Kaplan-Meier product-limit method and Greenwood's formula. A month will be calculated as time in days divided by 30.4375.

Table 1. Censoring Rules

Case	Censoring Rule
Patient has no post baseline assessments	Censor at date of first dose
and no date of death recorded	
Patient did not die or experience PD or	Censor at date of last adequate response
relapse*	assessment (any response assessment that is
	not "Not Evaluable" or "Not Done")
Patient in Phase 1 started on single agent	Censor at date of last adequate response
therapy, but switched to combination	assessment prior to the combination therapy
therapy	

*For patients who discontinue FT-2102 treatment to receive HSCT and remain on study to be followed until documented disease relapse, confirmation of relapse is not required in this situation, and a single occurrence of relapse will be considered as documented "confirmed" relapse in analyses of response.

The following sensitivity analyses of DCR/CRh will be performed with censoring rule variations in EE patients:

- 1. Patients who undergo HSCT will be censored at the last adequate assessment prior to HSCT
- 2. Patients who discontinued study treatment due to undocumented progression will be considered as events at the date of last dose
- 3. Patients with subsequent anti-cancer therapies prior to an event date will be considered to be censored the day before the start of the anti-cancer therapy.

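### The SAS code in SAP Appendix 2 does not carry out the analyses described in the SAP text: Kaplan-Meier is not split by cohort, CR/CRh is not derived, and one reference rate of 15% is printed for all cohorts

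*SAP*

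**What the plan says.** **Time-to-event text.** SAP section XI.B says that RFS, EFS, OS and the duration endpoints "will be analyzed using Kaplan-Meier (KM) methods for each cohort". It asks for survival probabilities at 3, 6, 12 and 24 months by the product-limit method with Greenwood's formula, and refers to Appendix 2 for the code.

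**Time-to-event code.** Appendix 2 B has two PROC LIFETEST steps. Each puts COHORT in an ID statement, and neither has BY or STRATA. The second, for OS, carries the options "plots=(s, ls, lls) intervals=3, 6, 12, 24".

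**CR/CRh text.** Section XI.A lists 14 investigator-assessed AML response categories and defines the CR/CRh rate as the proportion of patients with CRm, CRc, CR or CRh. Section IV.C sets the reference rates:
- Cohort 1: 15% ("seventy-three (173) patients provide 90% power to test the null hypothesis that the true complete response rate (CR + CRh) is 15% or less").
- Cohort 6: 15%.
- Cohorts 3-5: 10%.
- Cohorts 7 and 8: 25% ("The null hypothesis that the true complete response rate is 25% will be tested against a one-sided alternative").

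**CR/CRh code.** Appendix 2 A offers code "of the following form will be used for the CR/CRh rate estimate along with confidence interval". It is a PROC FREQ step with BY COHORT, the line "tables OUTCOME / exact binomial (p=0.15", and the definition "OUTCOME is a vector containing the investigator response for each patient".

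**The concern.** The SAP text sends the reader to Appendix 2 for both sets of analyses, so the code should deliver what the text describes. Run as printed on a dataset holding several cohorts, the LIFETEST steps would mix relapsed/refractory, MRD-positive and treatment-naive patients in one curve. Section VI.B treats these as different populations, to be summarised by cohort. The FREQ step would report the frequency of one response category in place of CR/CRh, and that reaches Cohort 1, the cohort with the group-sequential test. It would also print, beside five cohorts' results, a p-value against a rate the plan never set for them. At stake are whether the outputs can be verified against the plan, and whether a by-product p-value could be mistaken for a cohort's test.

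**Working it through.** The code was read, not run. Statements about what SAS does are general knowledge of the procedures, not something the documents describe.

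**1. Grouping in LIFETEST.** ID labels observations in the output and forms no groups; BY and STRATA form groups. With neither present, the step gives one product-limit curve for whatever is in the dataset. That meets XI.B only if the data are first cut to one cohort, and no such step is shown. INTERVALS= governs life-table intervals; TIMELIST= gives product-limit estimates at named times, which is what XI.B asks for.

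**2. The variable in FREQ.** The binomial option evaluates one level of the variable, by default the first. CR/CRh is the union of four levels (CRm, CRc, CR, CRh). No single level equals that union, so LEVEL= without a recode would not produce it either. No recode is shown. The step also weights by a count variable that is not defined.

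**3. The fixed 15%.** The plan's own figures reproduce first, using

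P(X ≥ r | n, p) = Σ from x = r to n of C(n,x) pˣ(1−p)ⁿ⁻ˣ.

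- Cohort 1, where "If exactly 173 patients are evaluable, this is equivalent to 36 or more responses observed": P(X ≥ 36 | 173, 0.15) = 0.0245, as stated. With the interim stops (≤6/58, ≤20/115, ≥28/115), type I error is 0.0245 and power at 25% is 0.907, against the stated 90%.
- Simon rules, Σ over x₁ > r₁ of P(X₁ = x₁)·P(X₂ ≥ r − x₁), at each cohort's own null and alternative, type I error / power: Cohort 6, 0.046 / 0.801; Cohort 7, 0.0245 / 0.804; Cohort 8, 0.021 / 0.811. All agree with section IV.C.

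Next, the one-stage exact p at the stated success counts, which is what FREQ would print once the variable is recoded:

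| Cohort | Count | Own null | p at own null | p at coded 15% |
|---|---|---|---|---|
| 1 | 36/173 | 15% | 0.0245 | 0.0245 |
| 3-5 (section IV.C count) | 4/20 | 10% | 0.133 | 0.352 |
| 3-5 (section XI.B count) | 5/20 | 10% | 0.043 | 0.170 |
| 6 | 11/44 | 15% | 0.057 | 0.057 |
| 7 | 20/54 | 25% | 0.033 | 0.00006 |
| 8 | 12/28 | 25% | 0.029 | 0.0004 |

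The printed value is too strong in Cohorts 7 and 8 and too weak in Cohorts 3-5. Cohorts 1 and 6 are right.

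**4. What does not depend on 15%.** The Clopper-Pearson 95% limits are beta quantiles, B(0.025; x, n−x+1) and B(0.975; x+1, n−x). The null rate does not enter. For example, 36/173 gives 15.0% to 27.6% and 20/54 gives 24.3% to 51.3%, whatever value of p is coded.

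**5. If the by-product were misread.** Suppose success in Cohorts 7 and 8 were taken from the coded p-value at one-sided 0.025. The cut-offs would fall to 15/54 and 9/28, from 20 and 12. With the stage 1 stop kept, type I error at a true 25% would be 0.162 and 0.122, against 0.025. The plan does not say to do this; the figures only bound the harm from a misreading.

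**The case against.** The strongest reply is that Appendix 2 is a template and the text governs. The FREQ code is offered as a form for the estimate and interval, not as the test. Section XI.B prescribes the one-sided exact test only for Cohort 1, where 15% is correct. Cohorts 3-5 are decided by an 85% interval against 10%, and Cohorts 6-8 by Simon counts. All of this stands. A reader might infer from the code that wrong nulls are used for decisions, or that response rates are pooled over cohorts. The documents do not support either reading: no planned decision uses the by-product p-value, and the FREQ step has BY COHORT.

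On LIFETEST, the dataset name is a placeholder, the efficacy tables in Appendix 3 are laid out by cohort, and curves are planned only for Cohort 1 (RFS for Cohort 2), so some subsetting is implied. On OUTCOME, the definition is loose and the count weight hints at pre-processed input. These make a correct implementation plausible. They do not put it in the plan: neither the subsetting nor the recode is written down.

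A further temptation is to replace 15% with each cohort's own null. For Cohorts 6-8 this would create a new conflict. At the stated rejection counts the one-stage p-values are 0.057, 0.033 and 0.029, each above its nominal level (0.05, 0.025, 0.025), although the two-stage rules reject there and hold their error rates. The one-stage tail ignores the stage 1 stop.

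**Conclusion.** Appendix 2 is wrong as written, in three respects of unequal weight. The LIFETEST code does not deliver per-cohort Kaplan-Meier estimates or product-limit landmarks. The FREQ code does not deliver the CR/CRh rate or its interval unless an unstated recode is made. The fixed 15% prints an irrelevant p-value for Cohorts 3, 4, 5, 7 and 8, off by a factor of roughly 550 in Cohort 7 (0.033 / 0.00006) and about 70 in Cohort 8 (0.029 / 0.0004) at the stated counts. The decision rules, their error rates and the Clopper-Pearson limits are untouched by the third item. The conclusion rests on standard SAS behaviour for ID, INTERVALS= and the binomial option, and on the code being applied as printed to a multi-cohort dataset with the response categories unrecoded.

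**What to change.** - **LIFETEST:** replace ID COHORT with BY or STRATA COHORT, and INTERVALS= with TIMELIST=3 6 12 24.
- **FREQ variable:** define a 0/1 indicator equal to 1 for CRm, CRc, CR or CRh, following section XI.A, and use LEVEL='1'. Define the count weight or remove it.
- **FREQ test:** keep the exact test at p=0.15 for Cohort 1 only. Suppress the one-stage test output for Cohorts 3-8 and cite the decision rules in sections IV.C and XI.B. Do not substitute cohort-specific one-stage p-values for Cohorts 6-8.

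Section IV.C (4 of 20) and section XI.B (5 of 20) give different counts for Cohorts 3-5. That is a separate matter, and suppressing the test output does not resolve it.

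The cost is a few lines in an appendix. No sample size, boundary or decision rule changes.

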Appendix 3 Column Headings for Analysis Tables

1. Data snapshots taken for the purpose of safety analysis (regulatory reporting, IB update, etc.) will be organized as follows:

Note: to be performed on data from both phase 1 and phase 2 patients, regardless of cohort #

2. Table generation for interim futility and efficacy analyses as well as final analyses will be organized as follows:

Phase 1:

Table xxx: Title xxx Analysis Set, Phase 1

	Single Agent		Combination: Azaci	Combination: Azacitidine 75 mg/m ² $$		
	FT-2102	Total	FT-2102	Total	Phase 1	
Parameter	150 mg BID	FT-2102	150 mg BID	FT-2102	Overall	

For Safety Tables:

Phase 2 Single Agent Therapy:

Table xxx: Title xxx Analysis Set, Phase 2 Single Agent

			FT-	-2102 150 mg H	BID	
					Phase 2	
					Single Agent	Ph.1 AML R/R
Parameter	Cohort 1	Cohort 2	Cohort 3	Cohort 7	Overall	& Ph.2 Cohort 1

Phase 2 Combination Therapy:

Table xxx: Title xxx Analysis Set, Phase 2 Combination Therapy

		FT-2102 150	mg BID + Azacitid	ine 75 mg/m²	
					Phase 2 Combination Therapy
Parameter	Cohort 4	Cohort 5	Cohort 6	Cohort 8	Overall

For Efficacy Tables:

Phase 2 Single Agent:

Table xxx: Title xxx Analysis Set, Phase 2 Single Agent

	FT-2102 150 mg BID				
Parameter	Cohort 1	Cohort 2	Cohort 3	Cohort 7	Ph.1 AML R/R & Ph.2 Cohort 1

Phase 2 Combination Therapy:

Table xxx: Title xxx Analysis Set, Phase 2 Combination Therapy

FT-2102 150 mg BID + Azacitidine 75 mg/m²

Parameter	Cohort 4	Cohort 5	Cohort 6	Cohort 8

DocuSign

Timestamp

Certified Delivery Events

Status

Carbon Copy Events	Status	Timestamp	
Witness Events	Signature	Timestamp	
Notary Events	Signature	Timestamp	
Envelope Summary Events	Status	Timestamps	
Envelope Sent	Hashed/Encrypted	2/19/2023 7:01:45 PM	
Certified Delivered	Security Checked	2/20/2023 3:01:41 PM	
Signing Complete	Security Checked	2/20/2023 3:02:20 PM	
Completed	Security Checked	2/20/2023 3:02:20 PM	
Payment Events	Status	Timestamps	
Electronic Record and Signature Disclosure			

CONSUMER DISCLOSURE

